## 1 INTRODUCTION

This document is a clinical investigations plan (CIP) for a clinical research study sponsored by Masimo Corporation. The study will be conducted in compliance with all stipulations of this plan, the conditions of IRB approval, ISO-14155 and International Conference on Harmonization Good Clinical Practice guidelines ICH E6 GCP.

### 1.1 Background and Rationale

The SedLine EEG monitor (Masimo Corporation, Irvine, CA) computes the following parameters: the Patient State Index (PSI) that is calculated via 4 channels of high resolution EEG data, EMG activity, and percent of EEG suppression.

Unlike most other non-invasive patient monitoring parameters, there is no gold standard or reference against which the SedLine/Patient State Index (PSI) could be compared. Hence, to evaluate performance of two algorithms, historically clinical outcome parameters such as post-surgery wake-up time, amount of anesthesia used, and frequency of somatic events were compared to evaluate algorithm performance.

The new (investigational) PSI is similar to the current (FDA-approved) PSI but has new features to compute PSI. The data collection study and methodology as described in this plan forms the basis for evaluating performance of the new (investigational) PSI against the current (FDA approved) PSI.

### 1.2 Study Devices

The FDA-cleared Masimo SedLine brain function monitor is indicated for use in the operating room (OR), intensive care unit (ICU), and clinical research laboratory. It is intended to monitor the state of the brain by real-time data acquisition and processing of electroencephalograph (EEG) signals. The system includes the Patient State Index (PSI™), a proprietary computed EEG variable that is related to the effect of anesthetic agents.

The Masimo Radical-7s and Root™ Rainbow Technology Multi-Function Docking Stations are indicated for the continuous non-invasive monitoring of Oxygen Saturation (SpO2), Pulse Rate (PR), Perfusion Index (PI), Pleth Variability Index (PVI), and either FDA-cleared PSI (Rev 1.x) or investigational PSI (Rev 2.x).

## 2 STUDY DESIGN AND OBJECTIVES

This is a prospective, single-center study with a total enrollment of up to 150 subjects.

### 2.1 Specific Aims

**Aim One:** to collect raw and processed EEG data with Masimo SedLine monitor while anesthesiologist is blinded to the PSI (Patient State Index) score and to the raw EEG waveforms from the Masimo SedLine monitor in order to establish a Baseline for Standard Practice.

**Aim Two:** to collect raw and processed EEG data with Masimo SedLine monitor while anesthesiologist is monitoring subject using the current (FDA approved) PSI to supplement Standard of Care (SOC) procedures in managing anesthesia.

**Aim Three:** to collect raw and processed EEG data with Masimo SedLine monitor while anesthesiologist is monitoring subjects using the new (investigational) PSI to supplement Standard of Care (SOC) procedures in managing anesthesia.

**Aim Four:** to evaluate the performance of the new (investigational) PSI compared to current (FDA approved) PSI. Comparison measures include frequency of somatic events, total anesthesia drug used, wake up times, PSI versus Observer's Assessment of Alertness/Sedation (OAA/S).

**2.2 Subjects will be assigned to one of three cohorts:**

- Cohort 1: The anesthesiologist will be blinded to the PSI score and the raw EEG data. Anesthetic management in be in accordance with SOC protocols and procedures.
- Cohort 2: The anesthesiologist will be monitoring subjects using the FDA-cleared PSI Rev 1.X.
- Cohort 3: The anesthesiologist will be monitoring subjects using the investigational PSI Rev 2.X.

**4 SUBJECT SELECTION AND WITHDRAWAL**

**4.1 Number of Subjects**

Up to 150 subjects undergoing general surgery may be enrolled into this study. Up to 50 subjects may be enrolled per Cohort.

**4.2 Inclusion Criteria**

- 18 years of age or older
- ASA status of I, II, and III
- Subjects undergoing general surgery
- Neurologically intact patients (e.g. no history or presence of traumatic brain injuries, neurological diseases, etc.)

**4.3 Exclusion Criteria**

- Subjects with any deformities, diseases or for any other reason that may prevent proper fit and application of the SedLine sensors.
- Inability to obtain subjects' physiological, vital, demographics, and real time anesthesia data.
- Subjects who are pregnant.
- Known history of drug abuse.
- Subjects deemed not suitable for study at the discretion of the Principal Investigator.

**4.4 Study Timelines**

Each individual patient will participate in one study visit. Each study visit may start only after the informed consent has been signed by the participant. The study visit will end in the OR upon patient wake up from anesthesia, at which point data collection is considered complete.

**4.5 Subject Recruitment and Screening**

Following identification of a potential subject, the patient will be approached by the principal investigator or a designated research staff member, who will explain the purpose and procedures of the study. If the patient express interest in participating in the study, they will be asked to read the written Informed Consent Form in English or Spanish depending on the patient's language preference.

All items of the Informed Consent will be explained in a way that is easily understandable, for either English or Spanish speaking subjects. The patient will be given adequate time to read through the Informed Consent, and they will be given adequate time and privacy to consider the decision of whether or not to sign the Informed Consent Form. Once all of the

patient's questions have been answered and the Informed Consent Form signed, the patient is now adequately consented. Now the patient will be enrolled as a study subject, at which time the subject will be assigned a study identification number or enrollment number.

All subjects will have their medical history reviewed at the time of screening by either the PI or the study staff who is delegated for this task. Subjects will be evaluated based on the inclusion and exclusion criteria to determine eligibility to be enrolled into the study. If a subject is deemed ineligible after screening, the subject will be withdrawn from the study.

Information regarding the subject's demographic (including, but not limited to age, weight, race, ethnicity, comorbidities, medications, etc.), preexisting allergies, skin abnormalities, and other preexisting diseases/conditions that may be relevant to the study will be recorded within a paper-based Case Report Form (CRF).

#### HIPAA

The pre-screening of patients will require the investigators to access personal health information to identify prospective subjects without HIPAA authorization prior to obtaining written informed consent for the study. Informed consent and HIPAA authorization will be obtained during recruitment and screening procedures as described in previous sections of this clinical investigation plan; however, pre-screening process would require a waiver of HIPAA authorization, as the research study could not be practicably carried out without this implied waiver of consent. The participants' rights and welfare will not be adversely affected by waiving consent. Patients' protected health information (PHI) will not be inappropriately reused or disclosed to any other person or entity. To further safeguard all protected health information, the data collected during the study will not be labeled with any personal identifying information, or with a code that this research team can link to personal identifying information. The data will not be stored with any protected health information identifiers.

#### **4.6 Withdrawal of Subjects**

Informed consent discussions will explicitly include emphasis that neither patient enrollment nor patient withdrawal from the study will result in any alterations to the standard clinical care. Subjects may elect to withdraw at any time up to the induction of general anesthesia.

### **5 STUDY DEVICE**

#### **Investigational Devices:**

- Masimo new/investigational Patient State Index (PSI).

#### **FDA-cleared Devices:**

- Masimo Radical-7 and Root™ Rainbow Technology Multi-Function Docking Station (Masimo Corp) equipped Oxygen Saturation (SpO2), Pulse Rate (PR), Perfusion Index (PI), Pleth Variability Index (PVI), and current/FDA approved Patient State Index (PSI).
- SedLine patient modules, cables, and sensors.
- Masimo SET Pulse Oximetry sensors.
- Laptop computer with data collection software [REDACTED]

#### **5.1 Device Accountability**

##### **5.1.1 Receipt of Study Device**

Upon receipt of the of the study device supplies, an inventory must be performed and the device accountability log filled out and signed by the person accepting the shipment. It is important that the designated study staff counts and verifies that the shipment contains all the items noted in the shipment inventory. Any damaged or unusable study devices in a given shipment

will be documented in the study files. The investigator must notify the study sponsor of any damaged or unusable study devices that were supplied to the investigator's site.

#### 5.1.2 Use of Study Device

Use of devices and sensors will be documented on case report forms for each subject.

#### 5.1.3 Return or Destruction of Study Device

At the completion of the study, there will be a final reconciliation of study devices and sensors shipped, devices/sensors used, and devices/sensors remaining. This reconciliation will be logged on the device accountability log. Any discrepancies noted will be investigated, resolved, and documented prior to return or destruction of unused study devices. Devices destroyed on site will only be upon written instruction from the sponsor and will be documented in the study files.

## 6 STUDY PROCEDURES

### 6.1 Cohort Enrollment

Each cohort will enroll up to 50 subjects each. Subjects will be assigned to Cohort 1 until up to 50 subjects have been enrolled, after which subjects will be enrolled to Cohort 2. Cohort 2 will enroll up to 50 subjects, after which subjects will be enrolled to Cohort 3, which will enroll up to 50 subjects. All Cohorts will have equal sample sizes.

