6.2.7 Where possible, the non-invasive data will be collected and stored continuously [REDACTED]  
[REDACTED] All other data not collected via continuous, automated data collection methods will be entered on to the paper Case Report Form (CRF).

6.2.8 Comparison measures including but not limited to somatic events, total anesthesia drug used, wakeup times, OAA/S scores and a review of the raw EEG data will be used to evaluate PSI algorithms.

### 6.3 Cohort 1

- 6.3.1 Raw data from all the study sensors will be collected as described in Section 6.2 (Non-invasive readings).
- 6.3.2 The anesthesiologist and/or anesthesia providers will be blinded to the PSI score and the raw EEG waveform. Anesthesia management will be in accordance with standard of care (SOC) practice.
- 6.3.3 All clinical interventions will be based on the institution's standard of care practices.
- 6.3.4 All study data as described in this Clinical Investigation Plan will be provided to Masimo and analyzed.
- 6.3.5 Raw EEG data may be retrospectively processed by candidate PSI algorithms.

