### **7 SAMPLE SIZE AND STATISTICAL CONSIDERATIONS**

In a two sample t-test, such as in this case when two different Cohorts (experimental vs. control) are being compared, the desired statistical power is usually set at 0.80. This convention implies a four-to-one tradeoff between  $\beta$  and  $\alpha$  ( $\beta$  is the probability of a Type II error (false negatives), and  $\alpha$  is the probability of a Type I error (false positives); 0.2 and 0.05 are conventional values for  $\beta$  and  $\alpha$ , respectively). The Cohen's d value, which is the expected difference between the means of the experimental group and the control group divided by the expected standard deviation, is usually set at 0.80. Assuming that experimental and control groups have equal sample sizes, and assuming that both groups have normal distributions, this combination of statistical power and Cohen's d yields an estimated sample size of 26 samples per Cohort/group.

The current clinical Investigation plan defines enrollment of up to 50 subjects per Cohort, which would provide more than enough samples per Cohort to detect a difference between the outcome variables of the different Cohorts.

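### All Rev 1.X subjects are enrolled before any Rev 2.X subject, so for three of the four Aim Four measures PSI version cannot be separated from calendar period

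*Combined protocol and SAP*

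**What the plan says.** Section 6.1 enrolls Cohort 1 to its limit, then Cohort 2, then Cohort 3: "Cohort 2 will enroll up to 50 subjects, after which subjects will be enrolled to Cohort 3, which will enroll up to 50 subjects". Under Sections 2.2, 6.4 and 6.5, providers see the cleared Rev 1.X in Cohort 2 and the investigational Rev 2.X in Cohort 3. Section 2 states: "This is a prospective, single-center study with a total enrollment of up to 150 subjects".

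Aims One to Three are data collection. Aim Four compares the new PSI with the current one: "Comparison measures include frequency of somatic events, total anesthesia drug used, wake up times", together with PSI against OAA/S. Section 1.1 says the study "forms the basis for evaluating performance of the new (investigational) PSI against the current (FDA approved) PSI".

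Section 7 derives the cohort size from a two-sample t-test that "yields an estimated sample size of 26 samples per Cohort/group", and says that up to 50 per cohort "would provide more than enough samples per Cohort to detect a difference between the outcome variables of the different Cohorts". Section 9.7 allows descriptive statistics, regression and accuracy measures, and allows Cohort 2 to be compared with Cohort 3. It commits to none of these and names no covariate or period term.

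On the EEG itself, Section 6.2.8 says "a review of the raw EEG data will be used to evaluate PSI algorithms", and Section 6.3.5, under Cohort 1 only, says "Raw EEG data may be retrospectively processed by candidate PSI algorithms".

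**The concern.** Each subject is managed under one PSI version. Somatic events, drug used and wake-up time depend on that management, so they can be compared only between subjects in different cohorts. With strictly sequential filling at one center, the Rev 1.X and Rev 2.X subjects come from periods that do not overlap, and no other site runs the other version at the same time. A change between the periods in surgical lists, staffing, drug practice or familiarity with the monitor would enter the Cohort 3 versus Cohort 2 difference in full.

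The stake is Aim Four. A difference could be credited to the new algorithm when it belongs to the period, and a shift in the opposite direction could hide a real one. Once Cohort 2 has filled, no analysis can restore the missing concurrency.

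**Working it through.** **Inputs.** From Section 7: d = 0.80, power 0.80, alpha 0.05, 26 per cohort. From Sections 4.1 and 6.1: up to 50 per cohort, equal sizes, sequential. Sidedness is not stated, so two-sided is assumed. The shift s, in SD units, is an assumption throughout because the documents give no drift figure. No version effect is assumed unless stated.

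**1. The plan's own figure.** For the two-sample t-test, df = 2n − 2 and noncentrality = d·√(n/2). At d = 0.80, power is 0.791 for n = 25 and 0.807 for n = 26, so 26 per cohort reproduces. At n = 50, power is 0.977.

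**2. Can a step be separated from version?** Take a model with an intercept, a Cohort 2 indicator and a Cohort 3 indicator, and add a step that begins at the Cohort 2 to Cohort 3 switch. The design matrix then has 4 columns but rank 3, because the step column equals the Cohort 3 column. The two effects cannot be estimated separately at any n. This does not depend on normality, so it also covers event counts.

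**3. What an unmodelled shift does.** Put s in place of d, so noncentrality = s·√(n/2). For s = 0.5 and n = 50 this is 0.5 × 5 = 2.5 on 98 df.

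| Assumed shift (SD) | Rejection rate, n = 26 | Rejection rate, n = 50 |
|---|---|---|
| 0 | 0.050 | 0.050 |
| 0.2 | 0.109 | 0.168 |
| 0.333 | 0.218 | 0.379 |
| 0.5 | 0.424 | 0.697 |

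Under a fixed shift the larger cohort is worse. If instead there is a true effect of d = 0.80 and the shift opposes it, the net difference is 0.80 − s:

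| Opposing shift (SD) | Power, n = 26 | Power, n = 50 |
|---|---|---|
| 0 | 0.807 | 0.977 |
| 0.2 | 0.564 | 0.844 |
| 0.333 | 0.379 | 0.637 |
| 0.5 | 0.186 | 0.318 |

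**4. Can enrollment order be used as a covariate?** A smooth trend can be modelled, at a price. With Cohorts 2 and 3 only, the correlation of cohort with enrollment order is 0.866, so the variance inflation is 1/(1 − 0.866²) = 4.0 and the standard error doubles (√4 = 2). On df = 2n − 3, power at d = 0.80 falls from 0.807 to 0.293 (n = 26) and from 0.977 to 0.508 (n = 50). The difference detectable with 80% power rises from 0.79 to 1.59 SD (n = 26) and from 0.57 to 1.13 SD (n = 50). Adding Cohort 1 and assuming one common slope gives inflation 3.0 and power 0.376 and 0.631.

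In simulation (20,000 runs), a linear trend that puts 0.333 SD between the cohorts gives rejection of 0.222 (n = 26) and 0.373 (n = 50) unadjusted, and 0.055 and 0.051 adjusted. A step of 0.333 SD at the switch is not removed: the mean adjusted estimate is 0.337 and 0.329, which is the whole step within simulation error.

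**5. Concurrent assignment.** With 100 subjects randomized 1:1 in blocks of 4 and a shift halfway through enrollment, simulated rejection is 0.049, 0.046, 0.044 and 0.037 for shifts of 0.2, 0.4, 0.5 and 0.8 SD, so at or below 5%.

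**The case against.** The best reply is that this is largely a data-collection study. No primary endpoint, hypothesis or success criterion is named, and Section 9.7 says only that cohorts may be compared. If the comparisons are read as descriptive, a clear limit on inference might be enough. That has some force, and it is why the fix includes a fallback. But Aim Four does state a version comparison, Section 1.1 says the study is the basis for it, and Section 7 plans to detect a difference between cohorts.

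Second, no drift is shown. This is true: the rejection rates follow entirely from assumed shifts. The finding that a step is not identifiable needs no numbers.

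Third, Section 7 is about power, and on its own assumptions it is right. That also stands. The point is only that sample size gives no protection against bias.

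Fourth, the plan permits regression and raw EEG is collected in all cohorts. Regression can handle measured case mix and, expensively, a smooth trend, but neither is specified. Reprocessing can rescue PSI against OAA/S, because both algorithms can run on the same recording. It cannot show what drug use or wake-up time would have been under the other version. Same-subject comparisons in Cohorts 2 and 3 may also not be neutral, since providers could manage anesthesia by the displayed version. The blinded Cohort 1 is the cleanest set.

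Finally, starting with Cohort 1 is defensible, because it secures the blinded baseline before any PSI is displayed in the study. That argument does not extend to separating Cohorts 2 and 3.

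**Conclusion.** The concern holds and should be fixed before Cohort 2 opens. For somatic events, total drug and wake-up time, a step at the switch or an unmeasured shift is inseparable from PSI version, whatever the sample size. That conclusion rests only on the enrollment order, the single center and the absence of any concurrent control in the available text.

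The size is conditional. It depends on the assumed shift and on a roughly normal outcome analyzed by t-test, which does not directly describe event frequency, and 50 per cohort is the upper case. With no shift there is no inflation, but enrollment order cannot show that no step occurred. PSI against OAA/S is not caught by this if both algorithms are run on the same EEG, which the plan offers only as an option and states only for Cohort 1.

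**What to change.** **(a) Section 6.1.** Enroll Cohort 1 first. When it is complete, randomize subjects 1:1 in permuted blocks, from a concealed list, to Cohort 2 (Rev 1.X) or Cohort 3 (one Rev 2.X build, identified and frozen before the first randomization). Providers will see which version is in use, so block sizes should vary and not be disclosed to them.

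*Cost:* an amendment and a list of up to 100 lines, with no extra subjects or visits. Both revisions must be on site together, and Rev 2.X must be ready when Cohort 2 starts. The documents give no readiness date, so this could delay Cohort 2. Providers using both versions in one period may carry habits across arms, which would dilute a difference.

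**(b) Section 9.7, whether or not (a) is adopted.** Prespecify that comparisons of the three outcomes are adjusted for pre-assignment variables: planned procedure, age, weight, comorbidities, medications and ASA status. Code them in advance into a few terms, because 52 to 100 subjects cannot support many. Case duration and other variables fixed after assignment should not be default covariates. If enrollment stays sequential, add a sensitivity analysis with enrollment order as a covariate and report its loss of precision. None of this removes an unmeasured period effect.

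*Cost:* analysis wording, plus one CRF field for planned procedure if the CRF does not already hold it.

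**(c) Section 6.3.5.** Extend it to all cohorts and make it a commitment: Rev 1.X and the frozen Rev 2.X build are both run on every subject's raw EEG, with PSI against OAA/S compared within subject and also reported by cohort.

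*Cost:* offline processing of recordings already collected.

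**(d) Reporting.** Label all comparisons with Cohort 1, and Cohort 3 versus Cohort 2 if enrollment stays sequential, as before/after comparisons that cannot be attributed to PSI version alone.

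*Cost:* wording only.

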### 6.2 Non-invasive readings

6.2.1 Subjects will be fitted with Masimo SedLine sensors per manufacturer's Directions for Use (DFU).

6.2.2 Subjects will be fitted with Masimo pulse oximetry sensors with Masimo SET per manufacturer's DFU.

6.2.3 The following non-invasive readings will be recorded for each study subject using the aforementioned sensors connected to Masimo Radical-7 and Root devices.

- Raw and processed EEG data, and the appropriate PSI parameter with Masimo SedLine
- SpO2, Pulse Rate, Perfusion Index (PI), and Pleth (PVI) with Masimo SET pulse oximetry

6.2.4 Observer's Assessment of Alertness/Sedation (OAA/S) will be assessed and recorded at regular intervals.

6.2.5 TIVA pump and/or bolus IV administration of anesthetic drugs will be recorded.

6.2.6 Inspired and end tidal anesthetic gas data will be recorded.

6.2.7 Where possible, the non-invasive data will be collected and stored continuously [REDACTED]  
[REDACTED] All other data not collected via continuous, automated data collection methods will be entered on to the paper Case Report Form (CRF).

6.2.8 Comparison measures including but not limited to somatic events, total anesthesia drug used, wakeup times, OAA/S scores and a review of the raw EEG data will be used to evaluate PSI algorithms.

### 6.3 Cohort 1

- 6.3.1 Raw data from all the study sensors will be collected as described in Section 6.2 (Non-invasive readings).
- 6.3.2 The anesthesiologist and/or anesthesia providers will be blinded to the PSI score and the raw EEG waveform. Anesthesia management will be in accordance with standard of care (SOC) practice.
- 6.3.3 All clinical interventions will be based on the institution's standard of care practices.
- 6.3.4 All study data as described in this Clinical Investigation Plan will be provided to Masimo and analyzed.
- 6.3.5 Raw EEG data may be retrospectively processed by candidate PSI algorithms.

